Appendix F Criteria for Potentially Clinically Significant Events

Table 12-7 Criteria for Potentially Clinically Significant Laboratory Tests

Parameter	PCS	Comments
Clinical Chemistry		
ALT	$\leq 3xULN$ *(Not a PCS criteria) $>3x - \leq 5xULN$ $>5x - \leq 8xULN$ $>3xULN$ $>5xULN$ $>8xULN$	FDA DILI Guidance Jul 2009.
AST	$\leq 3xULN$ *(Not a PCS criteria) $>3x - \leq 5xULN$ $>5x - \leq 8xULN$ $>3xULN$ $>5xULN$ $>8xULN$	FDA DILI Guidance Jul 2009.
ALT or AST	$ALT > 3xULN$ or $AST > 3xULN$	Vertex LFT working group 2014
Alkaline Phosphatase	$>1.5xULN$	FDA DILI Guidance Jul 2009.
Total Bilirubin	$>1.5x - \leq 2xULN$ $>2xULN$	FDA DILI Guidance Jul 2009.
ALT and Total Bilirubin	$ALT > 3xULN$ and $TBILI > 2xULN$	FDA DILI Guidance Jul 2009. To be counted within a same treatment phase, whatever the interval between measurement.
AST and Total Bilirubin	$AST > 3xULN$ and $TBILI > 2xULN$	FDA DILI Guidance Jul 2009. To be counted within a same treatment phase, whatever the interval between measurement.
(ALT or AST) and Total Bilirubin	$(ALT > 3xULN$ or $AST > 3xULN)$ and $TBILI > 2xULN$	Vertex LFT working group 2014

Table 12-8 Criteria for Potentially Clinically Significant Vital Signs

CRITERIA for POTENTIALLY CLINICALLY SIGNIFICANT VITAL SIGNS		
Parameter	PCS	Comments
HR	≤ 50 bpm and decrease from baseline ≥ 20 bpm ≥ 120 bpm and increase from baseline ≥ 20 bpm	To be applied for all positions (including missing) except STANDING.
SBP	>140 mmHg at least once >160 mmHg at least once >140 mmHg at least twice >10 mmHg increase from Baseline at least once >20 mmHg increase from Baseline at least once	To be applied for all positions (including missing) except STANDING.
DBP	>90 mmHg at least once >100 mmHg at least once >90 mmHg at least twice >5 mmHg increase from Baseline at least once >10 mmHg increase from Baseline at least once	To be applied for all positions (including missing) except STANDING.

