11.5 Safety

Safety evaluations will include AEs, clinical laboratory assessments, clinical evaluation of vital signs, ophthalmologic examinations (for subjects under 18 years of age only), and physical examinations (PEs). Spirometry data will also be used as safety-supporting data.

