12.3.4.4 Vital Signs

The following vital signs will be summarized by treatment group at each scheduled time point: systolic and diastolic blood pressure (mmHg), body temperature, pulse rate (beats per minute), and respiratory rate (breaths per minute). Clinically significant abnormal findings in vital signs will be reported as AEs.

The number and percentage of subjects who meet the abnormal criteria for the vital signs evaluation during the Treatment Period will be tabulated by treatment group: HR \leq 50 bpm and a decrease from baseline \geq 20 bpm, HR \geq 120 bpm and an increase from baseline \geq 20 bpm, systolic blood pressure \leq 95 mm Hg and a decrease from baseline \geq 20 mm Hg, systolic blood pressure \geq 160 mm Hg and an increase from baseline \geq 20 mm Hg, diastolic blood pressure \leq 45 mm Hg and a decrease from baseline \geq 10 mm Hg, diastolic blood pressure \geq 110 mm Hg and an increase from baseline \geq 10 mm Hg, weight \geq 5% increase from baseline, and weight \geq 5% decrease from baseline.

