12.3.4.6 Other Safety Analysis

Ophthalmologic examination findings will be listed.

Spirometry data will be summarized descriptively as safety-supporting data. The following summaries will be provided at each visit based on the Safety Set:

- Numbers and percentages of subjects with decrease of ≥ 5 percentage points and with decrease of ≥ 10 percentage points in absolute change from baseline in ppFEV₁ at each visit.
- Numbers and percentages of subjects with $\geq 5\%$ decrease and with $\geq 10\%$ decrease in relative change from baseline in ppFEV₁ at each visit.
- Numbers and percentages of subjects with decrease of ≥ 0.05 L and with decrease of ≥ 0.10 L in absolute change from baseline in FEV₁ at each visit.
- Numbers and percentages of subjects with $\geq 5\%$ decrease and with $\geq 10\%$ decrease in relative change from baseline in FEV₁ at each visit.

Subjects with decrease of ≥ 5 percentage points in absolute change from baseline in ppFEV₁ or absolute change from baseline in FEV₁ at any visit will be listed. The listing will include raw values and absolute/relative changes from baseline in FEV₁ and ppFEV₁ at all visits.

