4 INTRODUCTION

This SAP describes the planned final analyses for the Study VX15-809-112 data and is based on the

- approved clinical study protocol (Version 1.0, dated 15 January 2016),
- approved electronic case report form (eCRF) (dated 13 January 2017).

Study VX15-809-112 is a Phase 4, Randomized, Double-Blind, Placebo-Controlled, Parallel-Design Study of the Effect of Lumacaftor/Ivacaftor Combination Therapy on Exercise Tolerance in Subjects Aged 12 Years and Older With Cystic Fibrosis, Homozygous for the *F508del-CFTR* Mutation.

This SAP (Methods) documents the planned final statistical analyses of efficacy and safety introduced in the study protocol of VX15-809-112, and describes the corresponding data presentations. It also documents additional efficacy and safety analyses not specified in the protocol, which will provide supportive information to the scientific understanding of the drug entity.

The [REDACTED] Biostatistics Department will perform the statistical analysis of the efficacy and safety data under the supervision of Vertex Biometrics Department; SAS (Version 9.2, or higher) will be used to generate all statistical outputs (tables, figures, listings, and datasets). The SAP will be finalized and approved prior to the final clinical data lock and treatment unblinding for the study.

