6.2 Safety Endpoints

The safety endpoints are as follows:

- Adverse events
- Clinical laboratory
- Vital signs
- Pulse oximetry
- Physical examination
- Ophthalmologic findings (for subjects under 18 years of age only)

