9.4 Safety Analysis

The overall safety profile of study drug will be assessed in terms of the following safety and tolerability endpoints:

- Adverse events
- Clinical laboratory values (hematology, serum chemistry, urinalysis, and coagulation studies)

Safety endpoints will be analyzed based on the Safety Set. Only descriptive analysis of safety will be performed (i.e., no statistical testing will be performed).

The study period will be divided into 3 segments:

- The **pre-treatment period** is defined as the period after the informed consent/assent date and before the initial dosing of study drug.
- The **treatment-emergent period** is the period at or after the initial dosing (including day 1) of study drug to 28 days after the last dose of study drug.
- The **post-treatment period** is defined as the period after 28 days after last dose until the end of study.

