9.4.3 Vital Signs

For the vital signs measurements, the raw values and change from baseline values will be summarized by treatment group at each scheduled time point: systolic and diastolic blood pressure (mm Hg)

The number and percentage of subjects with at least one PCS vital signs event during the treatment-emergent period will be summarized. The PCS criteria are provided in Appendix F

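### The SAP omits without explanation the protocol's low-blood-pressure, 5% weight-change and FEV1-decline counts, leaving no table of measured falls past a threshold

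*SAP*

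**What the plan says.** **Protocol.** Section 12.3.4.4 commits to counts and percentages of those "who meet the abnormal criteria for the vital signs evaluation during the Treatment Period will be tabulated by treatment group". It then gives eight criteria: low and high heart rate, low and high systolic pressure, low and high diastolic pressure, and weight up or down by at least 5%. Each heart-rate and blood pressure criterion joins a level to a change from baseline. Section 11.5 adds that "Spirometry data will also be used as safety-supporting data". Section 12.3.4.6 makes that concrete: "The following summaries will be provided at each visit based on the Safety Set", followed by four pairs of decline thresholds for ppFEV1 and FEV1 and a listing of subjects with declines.

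**SAP.** Section 4 says the SAP "documents the planned final statistical analyses of efficacy and safety introduced in the study protocol of VX15-809-112". Section 9.4.3 says: "The number and percentage of subjects with at least one PCS vital signs event during the treatment-emergent period will be summarized". The criteria are those of Appendix F, Table 12-8, which has entries for heart rate, systolic pressure and diastolic pressure only. The blood pressure change criteria are of the form "mmHg increase from Baseline at least once". Section 9.4 states: "Safety endpoints will be analyzed based on the Safety Set". Its subsections cover adverse events, laboratory results, vital signs, pulse oximetry, physical examination and ophthalmology. Spirometry has no subsection there and is not in the list in section 6.2.

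**The concern.** The SAP presents itself as carrying out the protocol's safety analyses and adding others. It does not say that any are withdrawn. If followed as written, it would count blood pressure rises but not falls, would not count weight change in either direction, and would leave out the whole spirometry safety summary.

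At stake is a simple between-arm safety question: how many subjects in each arm had a marked fall in blood pressure, weight or FEV1. The protocol plans no interim analysis and no data monitoring committee (12.3.5), so the final tables are where the planned between-arm comparison of these measurements would appear.

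**Working it through.** The plan gives no figure to reproduce, so the check is an item-by-item comparison.

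**Vital signs and weight: Protocol 12.3.4.4 against SAP Table 12-8**

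| Protocol criterion | In SAP Table 12-8 |
|---|---|
| HR ≤50 bpm with fall ≥20 | Unchanged |
| HR ≥120 bpm with rise ≥20 | Unchanged |
| SBP ≤95 mm Hg with fall ≥20 | Absent |
| SBP ≥160 mm Hg with rise ≥20 | Split into separate level and rise rows |
| DBP ≤45 mm Hg with fall ≥10 | Absent |
| DBP ≥110 mm Hg with rise ≥10 | Split into separate level and rise rows; no row at 110 |
| Weight up ≥5% | Absent |
| Weight down ≥5% | Absent |

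Tally: 2 unchanged + 2 redefined + 4 absent = 8.

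The SAP has 5 systolic and 5 diastolic rows, 10 in all. Each set has 3 level rows (two thresholds met at least once, one met at least twice) and 2 rise rows. That gives 6 level rows, 4 rise rows and no fall row.

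An illustrative case: systolic pressure falls from 118 to 92 mm Hg. The fall is 118 − 92 = 26, which is at least 20, and 92 is at or below 95. The protocol criterion is met. No systolic row in Table 12-8 is met.

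**Spirometry: Protocol 12.3.4.6 against SAP 9.4**

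- The protocol's pairs are ppFEV1 absolute fall (≥5, ≥10 points), ppFEV1 relative fall (≥5%, ≥10%), FEV1 absolute fall (≥0.05, ≥0.10 L) and FEV1 relative fall (≥5%, ≥10%).
- 4 pairs × 2 thresholds = 8 counts per visit, plus 1 listing.
- In SAP 9.4.1 to 9.4.6, 0 of the 8 counts and 0 of the 1 listing appear.

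**What the SAP still shows**

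- Blood pressure: raw values and changes from baseline (9.4.3), with mean, SD, median, minimum and maximum (9.1).
- ppFEV1 and BMI: FAS efficacy models and descriptive summaries at Weeks 12 and 24 (9.3.2.2.2), with no threshold counts.
- FEV1 in litres: only a baseline characteristic (9.2.2) and the input to ppFEV1 (Appendix D).
- Weight after baseline: summarised only through BMI. The relative BMI ratio is (weight at visit ÷ weight at baseline) × (height at baseline ÷ height at visit)². Height is re-measured in subjects aged 21 or younger at Screening (Protocol Table 3-2, footnote c), so in them BMI change is not weight change.

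**Why these do not replace the counts.** A minimum describes one subject. In a planned arm of 33, the same minimum can arise with 1 subject past a threshold (1/33 = 3.0%) or with 5 (5/33 = 15.2%). This is an illustration, not a prediction. The mean, SD and median reported alongside do not give the count either.

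**Could the text be missing only from the public copy?** This is unlikely. The SAP contents page lists 9.4.1 to 9.4.6 with no spirometry section, the list of tables runs from 12-1 to 12-8 without a gap, and neither 9.4 nor Table 12-8 carries a redaction mark. Appendix E is absent from the lettering, but nothing in 9.4 points to it.

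**The case against.** The best case against giving this much weight runs as follows.

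- **Adverse event tables do count some falls.** The protocol has clinically significant vital-sign abnormalities and clinically significant worsening of assessments reported as adverse events. SAP 9.4.1 tabulates subjects by preferred term and adds a respiratory table. This stands, and it narrows the gap to measured falls against a threshold. Reporting depends on the investigator's judgement and does not reproduce those counts.
- **Nothing is lost from the data.** All subject data are listed, the trial has about 66 subjects, and spirometry after Day 1 is scheduled only at Weeks 12 and 24 and at early termination. A reader could count by hand. True, but that is not a pre-specified table.
- **BMI stands in for weight in older subjects.** If the last recorded height is carried forward, which the SAP does not state for BMI, relative BMI change equals relative weight change in subjects over 21. That is fair for this subgroup, though BMI is still not counted against a 5% threshold.
- **The high-pressure rows lose little.** Anyone meeting the protocol's joint high criterion also meets Table 12-8 rows with lower thresholds. Only the joint level-and-rise count disappears.
- **SAP 6.2 is weak evidence.** The protocol's own safety endpoint lists also leave out spirometry, treating it as supporting data. The argument rests on 12.3.4.6 and the content of SAP 9.4, not on 6.2.
- **The protocol leaves detail to the SAP.** Section 12 calls itself a summary. Deferring detail does not cover silently removing named tables.

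**Conclusion.** The concern holds. Against the protocol's commitments, the SAP keeps 2 of 8 vital-sign and weight criteria, redefines 2 and drops 4. It carries none of the 8 FEV1 and ppFEV1 decline counts per visit and not the listing. No reason is given, and SAP section 3 records no modifications. Spirometry still has analysis visit windows in Appendix C, which suggests oversight more than decision, though the documents do not settle that.

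The consequence is confined to descriptive safety reporting. No SAP table would give the number of subjects per arm whose measured blood pressure, weight or FEV1 fell past a protocol threshold, and the blood pressure count would look in one direction only. The primary and key secondary inferences are untouched. The conclusion rests on the text of the two documents and on no distributional or event-rate assumption. It is a point that should be corrected, not one that threatens the trial's main result.

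**What to change.** Reconcile the SAP with the protocol before data lock:

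1. Add the blood pressure and weight criteria of Protocol 12.3.4.4 to Table 12-8, including the joint level-and-rise form of the high-pressure criteria. The existing rows may stay as supplementary.
2. Add a subsection to SAP 9.4 with the ppFEV1 and FEV1 decline counts of Protocol 12.3.4.6 by visit and treatment group, and the listing, all on the Safety Set.
3. If any of these is dropped on purpose, say so in the SAP and give the reason.

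The cost is SAP wording, a few descriptive tables and one listing. For the two scheduled post-baseline visits, the spirometry table needs 8 × 2 = 16 count rows. All the data are already collected under the protocol schedule.

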Appendix G Important Protocol Deviation Programming Rules (Based on the Clinical Database)

Important protocol deviations before first dose

1. Individual screening assessment(s) that did not meet eligibility criteria, excluding the exceptions that are permitted per protocol, were repeated
2. Screening visit performed outside of the -28 to -1 day window
3. Subject randomized and screening ophthalmologic examination greater than 3 months prior to Screening Visit
4. Height not collected for subjects who were 21 years of age or younger at the Screening Visit.

Important protocol deviations during treatment period

5. ETT visit was less than 3 weeks after the last dose of study drug but no Safety Follow-up Visit was performed.
6. After subject study completion/early discontinuation, prior study visits not done
7. Subject who prematurely discontinues study drug treatment did not complete the ETT visit
8. CPET not performed per protocol schedule
9. Prohibited medication taken during study
10. Initial dose of study drug not administered on Day 1.
